#### 7. PLANNED ANALYSIS

The format of the listings and tables will follow the BI guideline "Standards for Reporting of clinical trials and project summaries" (6).

The individual values of all subjects will be listed. Listings will be sorted by treatment sequence, subject number and visit (if visit is applicable in the respective listing). AE listings will be sorted by assigned treatment (see Section 7.8.1 below for details). The listings will be contained in Appendix 16.2 (SDL) of the CTR.

The following standard descriptive statistical parameters will be displayed in summary tables of continuous variables:

N number of non-missing observations

Mean arithmetic mean SD standard deviation

Min minimum Median median Max maximum

For plasma concentrations as well as for all PK parameters the following descriptive statistics will additionally be calculated:

CV arithmetic coefficient of variation

gMean geometric mean

gCV geometric coefficient of variation

For PK parameters the following descriptive statistics will additionally be calculated:

P10 10th percentile Q1 1st quartile Q3 3rd quartile P90 90th percentile

The data format for descriptive statistics of plasma concentrations will be identical with the data format of the respective concentrations. The descriptive statistics of PK parameters will be calculated using the individual values with the number of decimal places as provided by the evaluation program. Then the individual values as well as the descriptive statistics will be reported with three significant digits in the CTR.

Tabulations of frequencies for categorical data will include all possible categories and will display the number of observations in a category as well as the percentage (%) relative to the respective treatment group. Percentages will be rounded to one decimal place. The category missing will be displayed if and only if there actually are missing values. Percentages will be based on all subjects in the respective subject set whether they have non-missing values or not.

#### 7.1 DEMOGRAPHIC AND OTHER BASELINE CHARACTERISTICS

Only descriptive statistics are planned for this section of the CTR.

#### 7.2 CONCOMITANT DISEASES AND MEDICATION

Concomitant diseases will be coded according to the most recent version of MedDRA. Concomitant medication will be coded according to the most recent version of the World Health Organisation – Drug Dictionary. Concomitant non-drug therapies will be coded according to the most recent version of MedDRA.

A medication will be considered concomitant, if it

- is ongoing at the time of first study drug administration, or
- starts within the analysis phase of the respective treatment (see Section 6.1 for a definition of treatments and analysis phases).

The relevance of the concomitant therapies to the evaluation of PK will be decided no later than at the RPM.

Only descriptive statistics are planned for this section of the CTR.

#### 7.3 TREATMENT COMPLIANCE

Treatment compliance will not be analyzed as a specific endpoint. Any deviations from complete intake will be addressed in the Report Planning Meeting (cf. Section 6.2) and described in the CTR.

#### 7.4 PRIMARY ENDPOINT

#### 7.4.1 Primary analysis of the primary endpoint

Primary analysis of the primary endpoint will be performed as defined in Section 7.3.1 of the CTP. The analysis will be based on the PKS.

To assess the relative bioavailability of extended release formulation compared with immediate release formulation on the PK of the treatment, the statistical model for the primary analysis defined in the CTP is an analysis of variance (ANOVA) model on the logarithmic scale including "sequence", "period" and "treatment" (formulation) as fixed effect and "subject nested within sequence" as random effect. All formulation data are included in the model for each pairwise comparison. The formulations T1 (62.5mg tab FRR fasted), T2 (62.5mg tab SRR fasted), T3 (62.5mg cap FRR fasted), and T4 (62.5mg cap SRR fasted) will be compared versus R1 (60mg tab IR fasted).

To assess the relative bioavailability of BI fed compared with BI fasted, the statistical model for the primary analysis defined in the CTP is an ANOVA model on the logarithmic scale including "treatment" as fixed effect and "subject" as random effect. The model will be analysed as a two period fixed sequence cross-over model. The formulations T5 (62.5mg tab SRR fed) will be compared versus T2 (62.5mg tab SRR fasted) and T6 (62.5mg cap SRR fed) versus T4 (62.5mg cap SRR fasted).

The relative bioavailability will be estimated by the ratios of the geometric means of (test/reference) of the primary endpoint.

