3. DESCRIPTION OF DESIGN AND TRIAL POPULATION

3.1 OVERALL TRIAL DESIGN AND PLAN

The study will be performed in healthy male subjects as an open-label, randomised, single-dose study in two parts. For a depiction of the overall study design, refer to Figure 3.1: 1.

[figure not shown]

Figure 3.1: 1

Example of the overall study design

Trial part 1 (n=24) will be performed as a five-period crossover design in order to compare test treatments T1 to T4 to the reference treatment R1. These treatments will be administered under fasted conditions and in one of the following 5 sequences, T3-R1-T1-T4-T2, T2-T1-T3-R1-T4, T4-T3-R1-T2-T1, T1-T4-T2-T3-R1, R1-T2-T4-T1-T3. Test treatments T5 or T6 will be added as the sixth treatment period. These treatments will be administered under fed conditions.

Trial part 2 (n=18) is optional and will be split in two parts. Trial part 2A will be performed as a three-period crossover design, with sequences T7-T8-R2, R2-T7-T8 and T8-R2-T7, to compare treatments T7 and T8 to the reference treatment R2. If appropriate, trial part 2B will follow as a two-period crossover design, with sequences T9-T10 and T10-T9, in order to compare test treatments T9 and T10.

A single dose of each treatment will be administered as follows:

Trial part 1

- R1-Reference Formulation 1: 60 mg BI 894416, fasted (n=24)
- T1-Prototype Formulation A2: 62.5 mg BI 894416, fasted (n=24)
- T2- Prototype Formulation C2: 62.5 mg BI 894416, fasted (n=24)
- T3- Prototype Formulation D2: 62.5 mg BI 894416, fasted (n=24)
- T4- Prototype Formulation F2: 62.5 mg BI 894416, fasted (n=24)

At least 10 subjects of part 1 (fixed sequence part)

- T5- Prototype Formulation C2: 62.5 mg BI 894416, after high-fat, high-calorie breakfast (n≥10)

Proprietary confidential information © 2020 Boehringer Ingelheim International GmbH or one or more of its affiliated companies

At least 10 of the other subjects of part 1 (fixed sequence part)

- T6- Prototype Formulation F2: 62.5 mg BI 894416, after high-fat, high-calorie breakfast (n≥10)

Decision point: either (a) stop here or (b) proceed to trial part 2A with either optimised formulations G (tablet) or I (capsule), as T7 under fasted conditions and T8 after a high-fat, high-calorie breakfast.

Decision rules:

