4. TREATMENTS

4.1 INVESTIGATIONAL TREATMENTS

The investigational products are manufactured by two different manufacturers:

- IR reference tablet: [REDACTED]
- ER tablet and ER capsule: [REDACTED]

BI 894416 doses will be calculated and administered as a free base, so the conversion factor is 1. The molecular weight of BI 894416 is 382.46 g/mol.

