7. STATISTICAL METHODS AND DETERMINATION OF SAMPLE SIZE

7.1 STATISTICAL DESIGN – MODEL

The main objective of this trial is to investigate the relative bioavailability of extended release formulations compared with the immediate release formulation, following oral administration under fasted and fed conditions on the basis of the primary and secondary pharmacokinetic endpoints, as listed in Sections [2.1.2](#) and [2.1.3](#).

In addition relative bioavailability between selected extended release formulations will be investigated. The trial is designed to allow intra-subject comparisons and will be evaluated statistically by use of a linear model for logarithmically transformed pharmacokinetic endpoints.

A further objective is to evaluate and compare further pharmacokinetic parameters between the treatments.

In addition the assessment of safety will be evaluated for the parameters specified in Section [2.2.2.2](#).

All parameters will be assessed descriptively.

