7.2 NULL AND ALTERNATIVE HYPOTHESES

The relative bioavailability of the reference formulation will be compared with the test formulations, the ratios of the geometric means (test/ reference), and their corresponding 2-sided 90% confidence intervals (CIs) will be provided. In addition, relative bioavailability between selected extended release formulations will be investigated in the same way as between test and reference. Since the main focus is on estimation and not testing, a formal hypothesis test and associated acceptance range is not specified.

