Point estimates for the ratios of the geometric means (test/ reference) for the primary endpoints (refer to Section [2.1](#)) and their two-sided 90% confidence intervals (CIs) will be provided.

The difference between the expected means for log(T)-log(R) will be estimated by the difference in the corresponding adjusted means (Least Squares Means). Additionally, their two-sided 90% confidence intervals will be calculated (which corresponds to the two one-sided t-test procedure, each at a 5% significance level) based on the residual error from the ANOVA and will be back-transformed to the original scale to provide the point estimate and 90% CIs for the ratio T/R.

Further exploratory analyses

The same statistical model as stated above will be repeated for the primary endpoints but with all sources of variation ('sequence', 'subjects within sequences', 'period', 'treatment') considered as fixed effects.

In addition to the model based approach all parameters will be calculated and analysed descriptively.

If an analysis model fails to converge or is not suitable, the model will be simplified.

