#### 6. GENERAL ANALYSIS DEFINITIONS

#### 6.1 TREATMENTS

For basic study information on treatments to be administered, assignment of treatment groups, and selection of doses, cf. Section 4 of the CTP.

The trial is divided into two parts but only trial part 1 was performed.

In **trial part 1**, each subject is planned to be treated in five subsequent treatment periods (five-period cross-over) with one single dose in each treatment period followed by one single dose in a sixth treatment period in a fixed sequence.

Treatments in the five-period cross-over:

- Reference treatment 1 (R1) 60mg tab IR fasted: 60 mg of BI 894416, IR tablets under fasted conditions
- Test treatment 1 (T1) 62.5mg tab FRR fasted:
   62.5 mg of BI 894416, ER tablet (fast release rate) under fasted conditions
- Test treatment 2 (T2) 62.5mg tab SRR fasted:
   62.5 mg of BI 894416, ER tablet (slow release rate) under fasted conditions
- Test treatment 3 (T3) 62.5mg cap FRR fasted:
   62.5 mg of BI 894416, ER capsule (fast release rate) under fasted conditions
- Test treatment 4 (T4) 62.5mg cap SRR fasted:
   62.5 mg of BI 894416, ER capsule (slow release rate) under fasted conditions

Each subject is planned to be randomly allocated to one of five treatment sequences (T3-R1-T1-T4-T2, T2-T1-T3-R1-T4, T4-T3-R1-T2-T1, T1-T4-T2-T3-R1 and R1-T2-T4-T1-T3, cf. Table 6.1: 2).

Treatments in the fixed sequence:

- Test treatment 5 (T5) 62.5mg tab SRR fed:
   62.5 mg of BI 894416 ER, tablet (slow release rate) after a high fat breakfast
- Test treatment 6 (T6) 62.5mg cap SRR fed:
   62.5 mg BI 894416, capsule (slow release rate) after a high fat breakfast

Subject will be randomly allocated to either T5 or T6, stratified by sequence (cf. Table 6.1: 2 for an overview of the treatment sequences).

For statistical analysis of AEs, safety laboratory data and vital signs, the following analysis phases are defined for each subject:

Table 6.1: 1 Flow chart of analysis phases for statistical analyses of AEs

Study analysis phase	Label	Start (inclusive)	End (exclusive)
Screening	Screening	Date of informed consent	Date/time of administration of BI 894416 in any formulation
On-treatment	BI 894416 respectively	Date/time of administration of BI 894416 in any formulation	Date/time of administration of BI 894416 in another formulation or 12:00 a.m. on day after subject's trial termination date, whichever occurs earlier

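### The four primary ER-versus-IR ratios are labelled relative bioavailability but compare 62.5 mg with 60 mg without dose normalisation, so each estimate and both 90% CI limits are 4.17% above the dose-normalised values.

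*SAP*

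**What the plan says.** SAP section 6.1 lists R1 as 60 mg of IR tablets, fasted. It describes T1 as "62.5 mg of BI 894416, ER tablet (fast release rate) under fasted conditions", and T2, T3 and T4 carry the same 62.5 mg dose. No salt correction offsets the difference, because Protocol section 4.1 states that "BI 894416 doses will be calculated and administered as a free base, so the conversion factor is 1".

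The primary endpoint is AUC0-∞ and the secondary is AUC0-tz (Protocol 2.1.2 and 2.1.3; SAP 5.1 and 5.2.2). Neither is defined per unit dose.

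Protocol 7.3.1 log-transforms the endpoint and fits sequence, subject within sequence, period and treatment. It then back-transforms the test-minus-reference difference, giving "Point estimates for the ratios of the geometric means (test/ reference) for the primary endpoints" with two-sided 90% confidence intervals. SAP 7.4.1 adopts this model for T1 to T4 against R1 and adds: "The relative bioavailability will be estimated by the ratios of the geometric means of (test/reference) of the primary endpoint". SAP 7.5.2 treats AUC0-tz the same way. The sensitivity analysis in SAP 7.4.2 refits the same models with all effects fixed. No dose term or dose-adjusted analysis appears in the visible text.

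**The concern.** Relative bioavailability compares the extent of absorption from two formulations. When the doses differ, a ratio of unadjusted AUCs combines the formulation effect with the dose difference.

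This matters because Protocol 7.1 says: "The main objective of this trial is to investigate the relative bioavailability of extended release formulations compared with the immediate release formulation". Protocol 7.2 adds: "Since the main focus is on estimation and not testing, a formal hypothesis test and associated acceptance range is not specified". In an estimation study, the size of the estimate and what it is called are the result. Protocol 4.1.2 also makes the need for dose modification depend on whether the extent of ER absorption differs from that of IR, which is the quantity the unadjusted ratio blurs. The shift has the same direction and size in all four comparisons, so a larger sample would not remove it.

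**Working it through.** The documents give no figure to reproduce. Protocol 7.7 says the sample size is not based on a power calculation, and Protocol 7.2 sets no acceptance range.

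**Inputs from the documents:** test dose 62.5 mg and reference dose 60 mg (SAP 6.1); common free-base scale (Protocol 4.1); natural-log analysis with back-transformed 90% CI (Protocol 7.3.1); n = 24 and five crossover periods (Protocol 3.1).

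**Step 1: size of the shift.** Dividing each AUC by its dose subtracts ln(62.5) from every test value and ln(60) from every R1 value. Each T − R1 log difference therefore changes by a constant, and its standard error does not change:

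- unadjusted ratio = dose-normalised ratio × 62.5/60 = dose-normalised ratio × 1.0417
- ln(62.5/60) = 0.0408
- dose-normalised ratio = unadjusted ratio × 60/62.5 = unadjusted ratio × 0.96

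For example, an unadjusted 1.00 becomes 0.960, 0.80 becomes 0.768 and 1.25 becomes 1.200. The excess is relative; it equals 4.17 percentage points only when the dose-normalised ratio is 100%.

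**Step 2: numerical check.** Data were simulated for the five planned sequences (5, 5, 5, 5 and 4 subjects), with assumed log-scale SDs of 0.2 within and 0.3 between subjects and about 5% of values missing (111 of 120 left). The planned mixed model and the all-fixed version were each fitted to log(AUC) and to log(AUC/dose). For every comparison, the estimate, lower limit and upper limit all differed by a factor of 1.04167. For T1 in the mixed model, 1.0535 (0.9621 to 1.1536) became 1.0114 (0.9236 to 1.1075).

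**Step 3: dependence on dose proportionality.** Step 1 is arithmetic and needs no pharmacokinetic assumption. Reading the factor as the dose's contribution to exposure does. If AUC scales as dose^b:

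- b = 0.8: (62.5/60)^0.8 = 1.0332, or 3.3%
- b = 1.2: (62.5/60)^1.2 = 1.0502, or 5.0%

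**Step 4: size relative to the precision.** The documents give no within-subject CV, so a range is assumed, and the design is treated as balanced. Residual df = 120 − 24 − 4 − 4 = 88; t(0.95, 88) = 1.662; σ_w = √ln(1 + CV²); SE = σ_w × √(2/24). Coverage is from the noncentral t distribution with ncp = 0.0408/SE.

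| Assumed CV | SE (log) | CI half-width factor | Shift ÷ log half-width | ncp | Coverage of dose-normalised ratio by nominal 90% CI |
|---|---|---|---|---|---|
| 15% | 0.0431 | 1.074 | 0.57 | 0.948 | 0.755 |
| 20% | 0.0572 | 1.100 | 0.43 | 0.714 | 0.816 |
| 30% | 0.0847 | 1.151 | 0.29 | 0.482 | 0.862 |
| 40% | 0.1112 | 1.203 | 0.22 | 0.367 | 0.878 |

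**Step 5: what is unaffected.** Contrasts among T1 to T4, T5 versus T2 and T6 versus T4 all compare 62.5 mg with 62.5 mg. The CI width on the log scale is also unchanged.

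**The case against.** The strongest reply is that nothing in the trial depends on this factor. Protocol 2.1.1 gives the main objective as choosing between tablet and capsule and then optimising, and those contrasts use equal doses. There is no acceptance range. The stop/continue rules in Protocol 3.1 use simulated steady-state Cmin, safety and preliminary pharmacokinetics, and SAP section 4 says the trial ended before anyone was treated in part 2. SAP 7.4.1 prints the dose beside each treatment, so a reader can multiply by 0.96. The coverage figures concern a different target: the interval keeps its nominal coverage for the AUC ratio the protocol defines.

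Dose-normalised AUC may also be among the further endpoints. Protocol 5.6 refers to a section 2.2.2.1 that is not in the available text, AUC0-24 is in the abbreviations but in no visible endpoint, and Protocol 7.3.3.1 analyses further endpoints as the primary one is analysed.

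Most of this stands, and it limits the impact. It does not settle the point. Protocol 7.1 states ER-versus-IR relative bioavailability as the main objective of the statistical analysis, and the visible primary and secondary analyses attach that name to a ratio of unequal doses. A withheld further endpoint might already supply the adjusted figures, but it would leave the primary result and its label as they are. That the correction is simple is a reason to make it in the report rather than leave it to each reader.

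**Conclusion.** The concern holds. The ratio planned for T1 to T4 against R1, for both AUC0-∞ and AUC0-tz, is an exposure ratio of the doses as administered. The estimate and both confidence limits exceed the dose-normalised values by a factor of exactly 62.5/60. Treating that excess as error in relative bioavailability rests on dose proportionality between 60 and 62.5 mg. With exponents from 0.8 to 1.2, dividing by dose would leave an error of only about 0.8% either way, since (62.5/60)^0.2 = 1.0082. How large the shift looks against the interval depends on a CV that the documents do not give. It should be fixed because it affects the label and size of a primary estimate, but it changes no in-trial decision rule.

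**What to change.** In SAP 7.4.1 and 7.5.2, report relative bioavailability for T1 to T4 versus R1 on AUC0-∞/dose and AUC0-tz/dose. Equivalently, subtract 0.0408 from each log difference, which multiplies the ratio and both limits by 0.96. Keep the protocol-defined unadjusted ratio beside it, labelled as the exposure ratio at 62.5 mg versus 60 mg as administered. State the dose-proportionality assumption. Leave T5 versus T2, T6 versus T4 and contrasts among T1 to T4 unchanged.

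The cost is one sentence in the SAP, one constant or derived variable, and one extra row per comparison; there are no new data and no model to refit. Because part 1 had been performed when the SAP was written, the addition should be listed in SAP section 4, which at present declares all analyses to be in line with the protocol. The constant is fixed by the design, so adding it late leaves no room for a data-driven choice.

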#### Exclusion of plasma concentrations

The ADS ADPC (PK concentrations per time-point or per time-interval) contains column variables ACEXC or ACEXCO indicating inclusion/exclusion (ACEXC) of a concentration and an analysis flag comment (ACEXCO). Exclusion of a concentration depends on the analysis flag comment ACEXCO. For example, if ACEXCO is set to "ALL CALC", the value will be excluded for all types of analyses based on concentrations. If ACEXCO is set to "DESC STATS" the value will be excluded from descriptive evaluations per planned time point/time interval. If ACEXCO contains the addition "TIME VIOLATION" or "TIME DEVIATION", the value can be used for further analyses based on actual times. If ACEXCO is set to "HALF LIFE", the value will be excluded from half-life calculation only; the value is included for all other analyses. Excluded concentration itself will be listed in the CTR associated with an appropriate flag.

#### Exclusion of PK parameters

The ADS ADPP contains column variables APEXC and APEXCO indicating inclusion/exclusion (APEXC) of a PK parameter and an analysis flag comment (APEXCO). All analyses based on the PKS are based on PK parameter values which are not flagged for exclusion, i.e. with APEXC equal to "Included".

Further details are given in "Noncompartmental Pharmacokinetic / Pharmacodynamic Analyses of Clinical Studies" (4) and "Description of Analytical Transfer Files and PK/PD Data Files" (5).

# 7.4.2 Sensitivity analysis, subgroup analysis, exploratory analysis of the primary endpoint

The same statistical model as used for the primary analysis for the comparison of formulations (Section 7.3.1 of the CTP) will be repeated for the primary endpoint but with all sources of variation ("sequence", "subject within sequence", "period" and "treatment" (formulation)) considered as fixed effects.

Similarly, the model used for the primary analysis for the comparison of BI fed versus BI fasted will be repeated for the primary endpoint with "subject" and "treatment" as fixed effect.

Furthermore, the primary PK endpoints will be assessed descriptively. The analysis of standard PK parameters is performed according to BI standards (4).

#### 7.5 SECONDARY ENDPOINT

#### 7.5.1 Key secondary endpoint

Not applicable.

#### 7.5.2 Secondary endpoint

The analysis of secondary endpoints will be based on the PKS.

TSAP for BI Trial No: 1371-0022

Proprietary confidential information © 2021 Boehringer Ingelheim International GmbH or one or more of its affiliated companies

The secondary endpoint will be statistically analysed in the same way as for the primary endpoint. The endpoint will also be assessed descriptively. The analysis of standard PK parameters is performed according to BI standards (4).

See Section 7.4 of this TSAP for details regarding exclusion of PK parameters and plasma concentrations.

#### 7.6.2 Safety parameters

Safety endpoints and tolerability will be analysed as described in Section 7.8 of this TSAP.

#### 7.7 EXTENT OF EXPOSURE

Descriptive statistics are planned for this section of the report.

#### 7.8 SAFETY ANALYSIS

All safety analyses will be performed on the TS.

